Post Authorization Safety Study (PASS) Information

Acronym/Title	Xarelto Paediatric VTE PASS Drug Utilization Study: An observational, longitudinal, multi-source drug utilization safety study to evaluate the drug use patterns and safety of rivaroxaban oral suspension in children under two years with venous thromboembolism (XAPAEDUS)
Protocol version and date	v 2.1, 16 NOV 2022
IMPACT study number	22195
Study type / Study phase	Observational  PASS Joint PASS:  YES  NO
EU PAS register number	Study not yet registered
NCT number	Study not yet registered
Active substance	B01AF01 Antithrombotic agents, Direct factor Xa inhibitors, Rivaroxaban
Medicinal product	Xarelto® 1mg/1mL granules for oral suspension
Product reference	EU/1/08/472/050-EU/1/08/472/051
Procedure number	EMA/H/C/000944
Comparator / Reference therapy	Standard of care (SOC); (heparins, vitamin K antagonists, other direct oral anticoagulants)
Study Initiator and Funder	Bayer AG
Research question and objectives	
The research question for this Post-Authorization Safety Study (PASS) is to evaluate the patterns of drug utilization and safety of rivaroxaban granules for oral suspension and of SOC in children under two years of age diagnosed with venous thromboembolism (VTE) and receiving anticoagulation therapy.
 
Primary objectives are to describe:
 
 Clinical characteristics and demographics of patients using anticoagulation therapy for the treatment of VTE (rivaroxaban oral suspension or SOC)

22195; XAPAEDUS; v 2.1, 16 NOV 2022;

Page 1 of 59

based on template version 9

	
 • Use of anticoagulation therapy (including selected drug, dose, and duration) for treatment of VTE • Incidence and severity of bleeding (major bleeding, and clinically relevant non-major bleeding) according to anticoagulation therapy (rivaroxaban oral suspension or SOC) 
Secondary objectives are to describe:
 
 • Time trends in patient characteristics and anticoagulation treatment patterns at the population-level over the study period • Incidence of recurrent symptomatic VTE according to anticoagulation therapy (rivaroxaban oral suspension or SOC) • Specialty and care setting of physicians who prescribe anticoagulation therapy (rivaroxaban oral suspension or SOC)

	Table 1: Milestones.....	15
	Table 2: Market presence of rivaroxaban granules for oral suspension 1 mg/mL (as of March 2022).....	21
	Table 3: Summary characteristics of data sources.....	29
	Table 4: Feasibility of study objectives in the data sources.....	30
	Table 5: Required number of patients by acceptable precision (95% CI) and proportions of interest using the exact approximation formula for CI for proportions.....	33
	Table 6: Estimation of patient counts.....	36
	Figure 1 Study design diagram.....	20
	Figure 2 Visualization of patient journey.....	23

2. List of abbreviations

ATC	Anatomical Therapeutic Chemical (Classification System)
CI	Confidence interval
CPR	Danish Civil Registration System
CRNM	Clinically relevant non-major
DCIR	Données De Consommation Inter-Régimes
DNPR	Danish National Patient Register
DOAC	Direct oral anticoagulant
DRG	Diagnosis Related Group
DUS	Drug utilization study
DVT	Deep vein thrombosis
EMA	European Medicines Agency
EMR	Electronic Medical Records
ENCePP	European Network of Centers for Pharmacoepidemiology and Pharmacovigilance
ERB	Ethical Review Boards
EU	European Union
GDPR	General Data Protection Regulation
GPP	Good Publication Practice
GVP	Good Pharmacovigilance Practice
ICD	International Classification of Diseases
LMWH	Low molecular weight heparin
LTD	Long-Term Chronic Disease
MAH	Marketing Authorization Holder
MBR	Medical Birth Register
NPR	National Patient Register
PASS	Post-Authorization Safety Study
PE	Pulmonary embolism
PIN	Personal Identification Number
PMSI	Programme de Médicalisation des Systèmes d'Information
QPPV	Qualified Person Responsible For Pharmacovigilance
RMPS	Register of Medicinal Products Statistics
SAP	Statistical Analysis Plan
SIDIAP	Sistema d'Informació per al Desenvolupament de l'Investigació en Atenció Primària
SMR	Hospital Patient Medication Register
SNDS	Système National Des Données De Santé
SOC	Standard of care
UFH	Unfractionated heparin

VKA Vitamin K antagonist
VTE Venous thromboembolism

3. Responsible parties

3.2. Contractors, Collaborators, Committees

Study feasibility and protocol development

Role: Project Manager

Name, Company: PPD [REDACTED] IQVIA

Role: Lead Epidemiologist

22195; XAPAEDUS; v 2.1, 16 NOV 2022;

based on template version 9

Page 7 of 59

Name, Company: PPD IQVIA

Role: Scientific Advisor

Name, Company: PPD IQVIA

Contact details of the responsible parties at IQVIA are kept as a stand-alone document ([Annex 1](#)).

Information on the Steering and Publication Committee Members and the respective Charters are kept as stand-alone documents ([Annex 1](#)).

Changes of responsible persons and/or the composition of the committees will be documented by updating the respective lists, but do not require formal protocol amendments.

4. Abstract

Acronym/Title	Xarelto Paediatric VTE PASS Drug Utilization Study: An observational, longitudinal, multi-source drug utilization safety study to evaluate the drug use patterns and safety of rivaroxaban oral suspension in children under two years with venous thromboembolism (XAPAEDUS)
Protocol version and date	v 2.1, 16 NOV 2022
IMPACT study number	22195
Study type / Study phase	 PASS Joint PASS:  YES  NO
Author	PPD [REDACTED] PPD [REDACTED] PPD [REDACTED] Bayer AG PPD [REDACTED] PPD [REDACTED] PPD [REDACTED] PPD [REDACTED] IQVIA PPD [REDACTED]
Rationale and background	Xarelto [®] (rivaroxaban), a direct oral anticoagulant (DOAC), was approved on JAN 2021 by the European Medicines Agency (EMA) for a new pharmaceutical formulation of granules for oral suspension 1 mg/mL, and for the indication in the paediatric population for treatment of venous thromboembolism (VTE) and prevention of VTE recurrence in term neonates, infants and toddlers, children, and adolescents aged less than 18 years. To supplement the limited information from the paediatric rivaroxaban clinical trial program in the youngest children, the EMA requested a category 3 post-authorization safety study (PASS) addressing the risk of bleeding in the young population. This drug utilization study will evaluate drug utilization patterns, bleeding, and recurrent VTE outcomes in children with VTE and under two years of age who are treated with rivaroxaban granules for oral suspension 1 mg/mL or standard of care (SOC) anticoagulation.
Research question and objectives	The research question for this PASS is to evaluate the patterns of drug utilization and safety of rivaroxaban granules for oral suspension and of SOC in children under two years of age diagnosed with VTE and receiving anticoagulation therapy. Primary objectives are to describe:

	
 • Clinical characteristics and demographics of patients using anticoagulation therapy for the treatment of VTE (rivaroxaban oral suspension or SOC) • Use of anticoagulation therapy (including selected drug, dose, and duration) for treatment of VTE • Incidence and severity of bleeding (major bleeding, and clinically relevant non-major bleeding) according to anticoagulation therapy (rivaroxaban oral suspension or SOC) 
Secondary objectives are to describe:
 
 • Time trends in patient characteristics and anticoagulation treatment patterns at the population-level over the study period • Incidence of recurrent symptomatic VTE according to anticoagulation therapy (rivaroxaban oral suspension or SOC) • Specialty and care setting of physicians who prescribe anticoagulation therapy (rivaroxaban oral suspension or SOC)
Study design	Observational, retrospective, descriptive, multi-national cohort study of new users of anticoagulation therapy conducted using secondary data sources
Population	The study population will consist of children aged under two years who initiate an anticoagulation therapy with rivaroxaban oral suspension or any other anticoagulation drug (index date) following a VTE diagnosis. Two exposure categories will be defined, one for rivaroxaban and one for SOC, and patients will contribute time to each exposure category if they switch from SOC to rivaroxaban or vice versa.
Variables	
Exposure
 
 • Recorded prescriptions or dispensed prescriptions of rivaroxaban oral suspension or SOC (heparins, vitamin K antagonists [VKAs] and other DOACs) • Data extracted from the data sources: 
 ○ Active substance ○ Route of administration

	
 ○ Date of prescription issuance (or filling) ○ Prescribed drug amount or days' supply ○ Prescribed daily dose (if available) ● Derived variables: 
 ○ Treatment episode by agent ○ Anticoagulation treatment period: sequence of treatment episodes of rivaroxaban and SOC ○ Drug switch(es) between anticoagulant agents within the same anticoagulation treatment period 
Primary outcomes
 
 ● Patient characteristics: 
 ○ Age, sex, and bodyweight at index date ○ Gestational age, if available ○ Characteristics of index VTE, if available ○ Co-morbidities before index date ○ Previous treatment before index date ○ Comedication during follow-up ○ Health resource utilization before index date ○ Duration of oral, nasogastric/gastric feeding before index date, if available ● Drug utilization patterns: 
 ○ Index drug therapy: substance and class of anticoagulant drug therapy, duration of use, dosing, route of administration ○ Maintenance therapy: substance and class of anticoagulant drug therapy, duration of use, dosing, route of administration ○ Switching to other anticoagulant therapy ○ Number and sequence of successive anticoagulation agents during an anticoagulant treatment period ● Safety outcomes: 
 ○ Major bleeding ○ Clinically relevant non-major (CRNM) bleeding
--	---

	
Secondary outcomes
 
 • Time trends by calendar year in patient characteristics and anticoagulation treatment patterns • Effectiveness outcome: recurrent symptomatic VTE • Specialty and care setting of the physician(s) who prescribe anticoagulation therapy
Data sources	
Due to the rarity of VTE in the targeted paediatric population and low incidence of the primary safety outcome, the planned data sources include existing secondary health data sources with broad coverage and/or population size.
 
According to the results of the feasibility study, the following data sources are planned to be included:
 
 • National health registers in Denmark and Sweden • Système National Des Données De Santé (SNDS) in France • Sistema d'Informació per al Desenvolupament de l'Investigació en Atenció Primària (SIDIAP) in Spain
Study size	
Based on the patient count estimations, the expected total study size in the four target countries (Denmark, France, Spain, and Sweden) is about 850 children under two years with VTE, with approximately 280 of them using rivaroxaban oral suspension.
 
All children from the target population present in the data sources will be analysed.

Data analysis	
Descriptive analyses by data source
 
Categorical variables will be presented as counts (n) and proportions (%), with 95% confidence intervals (CI) where relevant. Continuous variables will be presented as means with standard deviation and as medians with interquartile range, where appropriate.
 
The following descriptive analyses will be presented:
 
 • Patients' characteristics according to exposure category (rivaroxaban or SOC), with stratification on the status of exposure, i.e., initiators versus switchers • Drug utilization patterns of initial therapy and maintenance therapy (dose, frequency, route of administration, treatment duration, treatment switch)

	
 • Crude incidence rate, cumulative incidence and Kaplan-Meier analysis of the safety and effectiveness outcomes, using an as-treated exposure definition. Sensitivity analyses will be applied for the exposure (considering only the first treatment agent episode) and for the safety and effectiveness outcomes (considering a more restrictive definition). 
Combined descriptive analyses of aggregated data across data sources
 
 • Characteristics of patients and drug use patterns • Safety and effectiveness outcomes (if sample size allows)
Milestones	
Start of study period: market entry date of rivaroxaban oral suspension in each country
 
Start of data collection: 12 months from the PRAC endorsement of the full study protocol
 
End of data collection: Q2 2029
 
Study progress report: Annually, from Q4 2023 to Q4 2027
 
Final report of study results: Estimated Q4 2029
 
The annual progress reports will allow to monitor the uptake of rivaroxaban oral suspension and follow-up the number of patients for the study population as well as opportunities to finalize the study earlier.

5. Amendments

None

6. Milestones

Table 1 presents planned milestones for the project. These milestones are based on a timely review and approval of the project. Administrative changes to milestones due to delays in study preparation and enrolment do not require amendments to the protocol. Revised study timelines and milestones which do not constitute a need for a formal protocol amendment are tracked in a stand-alone document ([Annex 1](#)).

Table 1: Milestones

Milestone	Planned date
Start of study period	Market entry date of rivaroxaban oral suspension in each country
Start of data collection ^a	12 months from the PRAC endorsement of the full study protocol (*)
End of data collection ^b	Q2 2029
Study progress report 1	Q4 2023
Study progress report 2	Q4 2024
Study progress report 3	Q4 2025
Study progress report 4	Q4 2026
Study progress report 5	Q4 2027
Registration in the EU PAS register	Study to be registered after PRAC approval of the protocol
Final report of study results	Estimated Q4 2029

^a Date from which data extraction starts, in the case of secondary use of data.

^b Date from which the analytical dataset is completely available. The analytical dataset is the minimum set of data required to perform the statistical analyses leading to the results for the primary objective(s) of the study.

(*) Time needed for data access process in data sources (applications, approvals) and other tasks to launch the study.

Time lag for data availability in the different data sources is an essential element in estimating overall timelines for milestones and study completion. It is estimated that the achievement of the target study size would require data observed until end of 2027, with end of data extraction by Q1 2029 (due to long time lag in some data sources), end of data collection by Q2 2029 and final report by Q4 2029. However, one of the key objectives of the annual progress reports will be to identify

22195; XAPAEDUS; v 2.1, 16 NOV 2022;

Page 14 of 59

based on template version 9

opportunities to finalize the study earlier. In parallel with the follow-up of the overall uptake of rivaroxaban oral suspension, the number of children under two years with venous thromboembolism (VTE), and those among them receiving rivaroxaban oral suspension will be monitored annually in each data source as far as possible, and reported in annual progress reports. Due to small sample size and General Data Protection Regulation (GDPR) obligations to suppress small cell counts, the primary objective on the incidence and severity of bleeding is only feasible in the largest data source(s). The progress reports will also contain a status update of data source applications for approvals and any relevant amendments.

7. Rationale and background

7.1. Strategic rationale

Xarelto® (rivaroxaban), a direct oral anticoagulant (DOAC), was approved on 21 JAN 2021 by the European Medicines Agency (EMA) for a new pharmaceutical formulation of granules for oral suspension 1 mg/mL for the following paediatric indication: treatment of VTE and prevention of VTE recurrence in term neonates, infants and toddlers, children, and adolescents aged less than 18 years after at least 5 days of initial parenteral anticoagulation treatment (1). To supplement the limited information from the paediatric rivaroxaban clinical trial program in the youngest children, the EMA requested a category 3 post-authorization safety study (PASS) addressing the risk of bleeding in the young population. This drug utilization study (DUS) will evaluate drug utilization patterns, bleeding, and recurrent VTE outcomes in children with VTE and under two years of age who are treated with rivaroxaban granules for oral suspension 1 mg/mL or standard of care (SOC) anticoagulation.

7.2. Scientific background

VTE is a condition of forming a blood clot in the deep veins of the arm, groin, leg, jugular, caval, renal, and portal veins (known as deep vein thrombosis [DVT]). It may travel through the circulation and occlude the pulmonary vasculature (known as pulmonary embolism [PE]).

In the paediatric population, VTE is a rare condition, with an incidence of about 100 times lower than in adults. The annual incidence of VTE has been reported between 0.14 and 0.49 per 10,000 children in the community overall, and between 5.3 and 5.7 per 10,000 among hospitalized children (2). The distribution of events is bimodal with the majority occurring in neonates/infants and in adolescents. Paediatric VTE is rarely idiopathic; more than 80% of children who experience a VTE have one or more risk factors. The most important risk factor is the presence of a central venous catheter. Other factors include infection, immobility, trauma, malignancy, congenital heart disease, chronic inflammatory conditions, and thrombophilia (3). Risk factors for recurrent VTE include age at onset, absence of anticoagulant treatment, persistent venous occlusion, or presence of the prothrombin gene mutation (4). The risk of recurrence for paediatric VTE ranges from 7% to 20%, however, recurrence is uncommon if the underlying cause is removed or resolved.

The aim of VTE therapy is generally to prevent disease progression, prevent VTE recurrence and the development of sequelae such as post thrombotic syndrome. The type of anticoagulation and optimal duration of therapy in the paediatric population is not clearly defined. Due to a moderate level of evidence, treatment guidelines for paediatric VTE are mainly extrapolated from adult studies. The

current SOC includes parenteral treatment with unfractionated heparin (UFH) or low molecular weight heparin (LMWH) and oral anticoagulation with vitamin K antagonists (VKA). For children with idiopathic VTE, the suggested treatment duration has a minimum of 3 months and a maximum of 6 to 12 months. Children with recurrent unprovoked VTE are usually treated indefinitely(5).

Rivaroxaban is the first centrally approved oral anticoagulant product in the European Union (EU) for treatment of secondary prevention of VTE in children. Besides, this orally administered alternative requires less monitoring than existing SOC. Rivaroxaban should be initiated following at least 5 days of initial anticoagulation treatment with parenteral heparins, with dose and frequency of administration based on body weight. In children weighting less than 30 kg, rivaroxaban oral suspension is the only available formulation.

In the pivotal Phase III EINSTEIN Junior study, in the rivaroxaban group, during the main treatment period, a total of four (1.2%; 4/335) children had recurrent VTE, which occurred during heparinization in two children, during tablet treatment in one child, and during suspension treatment in one child. In the comparator group, a total of five (3.0%; 5/165) children had recurrent VTE, resulting in a hazard ratio of 0.40 (95% CI 0.11 – 1.41). All four recurrent VTEs in the rivaroxaban group occurred in the 184 children aged 12 to <18 years (6).

Like for the other anticoagulants, bleeding is an important identified risk for rivaroxaban. In the paediatric population, the safety evaluation of rivaroxaban was mainly based on the pivotal Phase III EINSTEIN Junior study(6). Among 491 included children (329 rivaroxaban, 162 comparator), the incidence of the principal safety outcome during the main treatment period (major bleeding + clinically relevant non-major [CRNM] bleeding) was numerically higher in the rivaroxaban group (10 children, 3%; all CRNM bleeding) compared to the comparator group (three children, 1.9%; two major bleeding, one CRNM bleeding). In the youngest children aged less than two years, there were only 53 patients included (21 and 9 [0.5 to <2 years] and 15 and 8 [<0.5 year], in rivaroxaban and comparator groups, respectively), with two patients (5.6%) in the rivaroxaban group and one patient (5.9%) in the comparator group having a CRNM bleeding. Furthermore, the coagulation system in neonates and infants aged <6 months is different from older children and adults, and extrapolation from adults is less straightforward than for elderly children (1).

Thus, although the pivotal Phase III EINSTEIN Junior study showed similar low risk of recurrent VTE without significant increased risk in bleeding with rivaroxaban compared to SOC, the experience of using rivaroxaban in children younger than 2 years is limited and safety data in this population is lacking in the real-world setting. The results from this PASS are intended to address this need for real-world data by characterizing drug utilization patterns, bleeding leading to hospitalization, and recurrent symptomatic VTE in clinical practice in children less than 2 years of age with VTE who are treated with rivaroxaban or other anticoagulants.

8. Research questions and objectives

This proposed PASS study is intended to evaluate the patterns of drug utilization and safety of rivaroxaban granules for oral suspension and of SOC in children under two years of age diagnosed with VTE and receiving anticoagulation therapy.

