9.2.3. Selection criteria

9.2.3.1. Inclusion criteria

Participants are eligible to be included in the study only if all of the following criteria apply:

- Evidence of initiation of an anticoagulant therapy (index drug), either rivaroxaban oral suspension or other anticoagulation therapies (heparins, VKAs, other DOACs). Initiation will be defined as a first record of any anticoagulation therapy (rivaroxaban or SOC) without any anticoagulation therapy in the previous 6 months, or since date of birth for children less than 6 months (see codes for anticoagulant drugs in [Annex 3](#)).
- Evidence of a prior VTE diagnosis (index VTE), defined as the presence of at least one primary/main or secondary diagnosis code for VTE recorded in inpatient setting in the previous 30 days (see preliminary list for VTE codes in [Annex 3](#)).
- Age less than two years on index date.
- Baseline period for availability of patient data history in the data source. A minimal baseline period of six months before index date for children aged between six months and two years, and a baseline period since birth for children less than six months of age will be required.

According to its indication, rivaroxaban oral suspension should be used after at least five days of initial parenteral anticoagulation treatment. In order to describe the actual clinical practice in real world settings, there will no requirement on this initial parenteral anticoagulation treatment to include patients in the study population, so patients will be identified independently of this. In theory, all patients receiving rivaroxaban should be switchers. In practice, they may appear as initiating directly with rivaroxaban: the observed initial anticoagulant therapy might be different from the actually received initial therapy, if patients have switched drug during hospital stay and if inpatient drug data is not captured. Depending on availability of inpatient drug data in each data source, the observed initiation of the anticoagulant therapy will be identified either in outpatient or in inpatient setting, as shown in [Figure 2](#) below (see [Section 9.4](#)).

SOC for treatment of VTE in children usually include UFH, LMWH and VKA and may vary across countries. With other DOACs receiving indication for VTE in paediatrics, SOC may also evolve over time.

Figure 2 Visualization of patient journey

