9.3.2.2.2. Effectiveness outcome

A secondary outcome on effectiveness will be recurrent symptomatic VTE.

Potential cases will be identified using diagnostic codes according to the different coding systems in the data sources (preliminary list in [Annex 3](#)). Care for children with an incident VTE takes place in inpatient setting (i.e., hospital stay requiring at least one night). At the same time, it is highly likely that VTE diagnoses are recorded as complications, secondary to other main reasons for a hospital stay. Therefore, the main definition for VTE diagnoses will be based on a sensitive approach including all primary/main and secondary diagnoses captured during hospitalization. Thus, a case of recurrent symptomatic VTE will be defined as a hospitalization with one of the following primary, related or associated diagnoses:

- DVT
- PE
- Cerebral vein or sinus thrombosis
- Central venous catheter related thrombosis
- Any VTE resulting in death.

A sensitivity analysis is planned for VTE outcome with a more restrictive definition using only main/primary diagnostic codes, excluding secondary diagnostic codes.

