Annex 3: Additional information

ATC codes for anticoagulant drugs

Class	Drug name	ATC code
1. Parenteral anticoagulants	Heparin	B01AB01
	Enoxaparin	B01AB05
	Dalteparin	B01AB04
	Nadroparin	B01AB06
	Tinzaparin	B01AB10
	Reviparin	B01AB08
	Parnaparin	B01AB07
	Bemiparin	B01AB12
	Fondaparinux	B01AX05
	Danaparoid	B01AB09
	Bivalirudin	B01AE06
	Argatroban	B01AE03
	2. Vitamin K antagonists	
Warfarin		B01AA03
Phenprocoumon		B01AA04
Acenocoumarol		B01AA07
Dicoumarol		B01AA01
Tiocloamarol		B01AA11
Ethyl biscoumacetate		B01AA08
Fluindione		B01AA12
Phenindione		B01AA02
Chlorindione		B01AA09
Diphenadione	B01AA10	
3. Direct oral anticoagulants	Rivaroxaban	B01AF01
	Dabigatran	B01AE07
	Apixaban	B01AF02
	Edoxaban	B01AF03

ATC = Anatomical Therapeutic Chemical (Classification System)

Codes for VTE (preliminary list)

Condition	ICD-10 or procedure code beginning with
VTE (composite)	I26, I801-802

ICD = International Classification of Diseases; VTE = Venous Thromboembolism

Codes for bleeding (preliminary list)

Condition	ICD-10 or procedure code beginning with
Intracranial bleeding	I60-62, S064, S065, S066, S067, S068
Gastrointestinal bleeding	I850, I983, K226, K250, K252, K254, K256, K260, K262, K264, K266, K270, K272, K274, K276, K280, K284, K286, K290, K625, K661, K920, K921, K922
Urogenital bleeding	N02, R319, N95
Other bleeding	H431, R04, R58, D629, procedure code DR029

ICD = International Classification of Diseases

Further details to the data sources

France - SNDS

SNDS contains information on beneficiaries age, sex, region of residence, death date, complementary universal health coverage status, and all outpatient healthcare consumption including all reimbursed prescription drugs identified by their ATC code, the date of delivery, quantity, and brand name. Medical procedures performed on an outpatient basis or in a healthcare institution are identified by the *classification commune des actes médicaux* (CCAM, or common classification of medical procedures), laboratory procedures are identified by the *nomenclature des actes de biologie médicale* (NABM, clinical pathology test nomenclature), and paramedical or medical visits are identified by the *nomenclature générale des actes professionnels* (NGAP, General nomenclature of professional procedures).

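### The only VTE code list, used for both cohort entry and recurrent VTE, covers pulmonary embolism and deep leg veins but not the other sites the protocol itself counts as VTE

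*Protocol*

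**What the plan says.** Section 7.2 gives the protocol's description of the disease: "VTE is a condition of forming a blood clot in the deep veins of the arm, groin, leg, jugular, caval, renal, and portal veins", with PE as its complication. It also says of children with VTE: "The most important risk factor is the presence of a central venous catheter".

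Section 9.2.3.1 makes cohort entry depend on a preceding VTE record. That record is "defined as the presence of at least one primary/main or secondary diagnosis code for VTE recorded in inpatient setting in the previous 30 days", and the criterion sends the reader to Annex 3 ("see preliminary list for VTE codes in").

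Section 9.3.2.2.2 defines recurrent symptomatic VTE by five components: DVT, PE, "Cerebral vein or sinus thrombosis", "Central venous catheter related thrombosis", and any fatal VTE. It relies on the same annex for its codes: "Potential cases will be identified using diagnostic codes according to the different coding systems in the data sources (preliminary list in" (the reference that closes this sentence is to that annex).

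The table in Annex 3 headed "Codes for VTE (preliminary list") has a single row, labelled as a composite and matched on the start of the code: I26, I801-802. No other VTE code list appears. Annex 1 records that the detailed variable list is not yet available and points back to Annex 3.

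**The concern.** One row of codes decides who is in the study and which later events count as recurrences, and it is narrower than the disease the protocol describes. If it were applied as printed, children treated for thrombosis only in an arm, jugular, caval, renal, portal or cerebral vein would be left out of every objective, because every objective is analysed in the cohort this row defines. Two of the five named recurrence components would have no code of their own.

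The omission also falls where paediatric disease is expected. The protocol names the central venous catheter as the leading risk factor, and section 9.3.2.1.1 plans to describe site and catheter-related thrombosis for the index VTE.

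No planned analysis would reveal the loss. The sensitivity analysis in section 9.7.6.3 only narrows the outcome to main diagnoses; nothing widens or tests the index diagnosis. The patient counts monitored under section 9.5.3, which decide when analyses are launched, could be affected as well.

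**Working it through.** **Step 1: set the definitions beside the codes.** The documents do not spell out the code meanings. In standard ICD-10, I26 is pulmonary embolism, I80.1 is the femoral vein, and I80.2 is other deep vessels of the lower extremities.

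| Site or component | Where named | Covered by I26, I801-802? |
|---|---|---|
| PE | 7.2, 9.3.2.2.2 | Yes |
| Groin and leg deep veins | 7.2 | Yes |
| Arm, jugular, caval, renal, portal veins | 7.2 | No |
| Cerebral vein or sinus | 9.3.2.2.2 | No |
| Catheter-related thrombosis | 9.3.2.1.1, 9.3.2.2.2 | No code of its own; caught only if a leg-vein or PE code is also recorded |

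**Step 2: reproduce the plan's counts.** Inputs from section 9.5.2 and Table 6: VTE incidence 0.14 to 0.49 per 10,000; share under two years 20% to 25%; market shares 10, 32, 38, 42, 50 and 30%.

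- Ratio of highest to lowest estimate: (0.49 × 0.25) / (0.14 × 0.20) = 4.375. For SNDS, 242 × 4.375 = 1,059 (stated 1,058).
- SNDS average: (242 + 1,058) / 2 = 650 (stated 650).
- Overall average: (315 + 1,376) / 2 = 845.5 (stated 846).
- Mean market share: 2.02 / 6 = 0.3367. Rivaroxaban users: 846 × 0.3367 = 284.8 (stated 285).
- SNDS rivaroxaban users: 650 / 6 × 2.02 = 218.8 (stated 219). Bleeds at 5.6%: 218.8 × 0.056 = 12.25 (stated 12).

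The table is internally consistent. Its starting point is VTE incidence with no site restriction stated.

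**Step 3: effect of an excluded share s.** The documents do not give s, so this is an assumed range. It supposes that the counts cover all sites, and that s and the bleeding risk are the same in all groups and data sources. Each count is multiplied by (1 − s).

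| s | Children (846) | Rivaroxaban users (284.8) | SNDS rivaroxaban bleeds (12.25) |
|---|---|---|---|
| 10% | 761 | 256 | 11.0 |
| 20% | 677 | 228 | 9.8 |
| 50% | 423 | 142 | 6.1 |
| 80% | 169 | 57 | 2.5 |

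**Step 4: where a threshold is crossed.**

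- French disclosure limit (section 9.7.8: counts under ten are suppressed): 12.25 × (1 − s) < 10 when s > 1 − 10/12.25 = 0.184, about 18%. Table 4 rates SNDS as the only source where the bleeding objective is feasible.
- Target of 29 rivaroxaban users per data source (section 9.5.3), Sweden: 33 × (1 − s) < 29 when s > 1 − 29/33 = 0.121, about 12%.

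**The case against.** The strongest reply is that the list is openly provisional. It is called preliminary at cohort entry, at the outcome and in its own title; section 9.7.1 leaves variable definitions to an analysis plan written before extraction; and section 9.3.2.2.2 already foresees different coding systems by source. The body text for the outcome is broad, so this may be an appendix that lags behind the text. That is fair. A reader might infer that these children can never enter, or that a leg-and-lung cohort was chosen on purpose. The documents support neither: the list can still change, and a child who also has a PE or deep leg-vein code would enter even now. The label does not remove the conflict, though. This is not a detail left open but a printed list that contradicts the protocol's own definitions.

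The second reply concerns size, and it largely stands. The excluded share is unknown, and so is the site mix behind the incidence figure, so one cannot say that 846 is wrong, only that it may be too high. The protocol's own range for SNDS rivaroxaban bleeds is 5 to 20, so a count under 10 is possible without any coding loss. It is also tempting to say that any loss puts the Spanish source below the selection floor of 15 in section 9.4.1. Unrounded, its expectation is 45 / 6 × 2.02 = 15.15, so the loss must exceed about 1%. That floor was also a criterion for choosing sources, not an analysis threshold.

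The third reply is that section 9.3.2.1.1 describes VTE site only if available. That excuses coarse reporting by site, not leaving children out at entry.

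**Conclusion.** The point holds as an inconsistency within the protocol that should be resolved before any data are counted or extracted. As written, the single Annex 3 row identifies PE and deep leg-vein thrombosis only. It has no code for five vein sites named in section 7.2 or for two recurrence components named in section 9.3.2.2.2. A child with only such a code would not enter, and a recurrence with only such a code would not be counted.

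The consequence for study size is possible but not quantified by the documents. The 18% and 12% tipping points are illustrations that rest on the average estimates in Table 6, on counts that cover all sites, and on a uniform excluded share. They are not estimates of the actual loss. The conclusion also relies on the standard ICD-10 meanings of three code stems.

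**What to change.** Before any patient counts or extraction, reconcile Annex 3 with sections 7.2 and 9.3.2.2.2:

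- Keep I26 and I801-802, and add codes for portal vein thrombosis, other venous thrombosis (caval, renal, upper-limb, jugular), cerebral vein or sinus thrombosis, and catheter-related thrombosis. Accept device-complication codes only when paired with a thrombosis code.
- Give source-specific equivalents for SIDIAP, which Table 3 lists as using ICD-9 and ICD-10-CM.
- Use the same list for index and recurrent VTE, and tabulate both by site.
- Admit the non-specific phlebitis codes I803, I808 and I809 only after coding review, or in a sensitivity analysis of cohort entry. They do not specify a deep vein, and the existing main-diagnosis sensitivity analysis covers the outcome only.
- State in section 9.5.2 that the Table 6 counts assume a list covering all sites.

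The cost is a revised annex table, matching text in the analysis plan and some coding review; no new data are needed. The downside is slightly lower specificity of the index diagnosis.
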